Progressive disease ⁹	
Appearance of a new splenomegaly that is palpable at least 5 cm below the LCM, OR
 
A $\geq 100\%$ increase in palpable distance, below LCM, for baseline splenomegaly of 5 to 10 cm, OR
 
A 50% increase in palpable distance, below LCM, for baseline splenomegaly of >10 cm, OR
 
Leukemic transformation confirmed by a bone marrow blast count of $\geq 20\%$, OR
 
A peripheral blood blast content of $\geq 20\%$ associated with an absolute blast count of $\geq 1 \times 10^9/L$ that lasts for at least 2 weeks

Stable disease	Belonging to none of the above listed response categories
Relapse	
No longer meeting criteria for at least CI after achieving CR, PR or CI, OR
 
Loss of anemia response persisting for at least one month, OR
 
Loss of spleen response persisting for at least one month

Key: CT = computed tomography; EMH = extramedullary hematopoiesis (no evidence of EMH implies the absence of pathology- or imaging study-proven non-hepatosplenic EMH); LCM = left costal margin; MRI = magnetic resonance imaging; UNL = upper normal limit

¹ Baseline and post-treatment bone marrow slides are to be stained at the same time and interpreted at one sitting by a central review process. Cytogenetic and molecular responses are not required for CR assignment.

² Grading of myelofibrosis is according to the European classification (*Thiele et al. Haematologica 2005;90:1128*). It is underscored that the consensus definition of “a complete remission bone marrow” is to be used only in those patients where all other criteria, including resolution of leukoerythroblastosis, are met. It should also be noted that it was a particularly difficult task for the working group to reach a consensus regarding what represents a complete histological remission.

³ Immature myeloid cells constitute blasts + promyelocytes + myelocytes + metamyelocytes + nucleated red blood cells. In splenectomized patients, $<5\%$ immature myeloid cells is allowed.

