⁴ See table 15 for definitions of anemia response, spleen response and progressive disease. Increase in severity of anemia constitutes the occurrence of new transfusion dependency or a ≥ 20 g/L decrease in hemoglobin level from pre-treatment baseline that lasts for at least 12 weeks. Increase in severity of thrombocytopenia or neutropenia is defined as a 2-grade decline, from pre-treatment baseline, in platelet count or absolute neutrophil count, according to Common Terminology Criteria for Adverse Events (CTCAE) version 4.0. In addition, assignment to clinical improvement (CI) requires a minimum platelet count of $\geq 25,000 \times 10^9/L$ and absolute neutrophil count of $\geq 0.5 \times 10^9/L$.

⁵ Applicable only to patients with baseline hemoglobin of <100 g/L. In patients not meeting the strict criteria for transfusion-dependency at the time of study enrollment (see below), but have received transfusions within the previous month, the pre-transfusion hemoglobin level should be used as the baseline

⁶ Transfusion dependency before study enrollment is defined as transfusions of at least 6 units of packed red blood cells (PRBC), in the 12 weeks prior to study enrollment, for a hemoglobin level of <85 g/L, in the absence of bleeding or treatment-induced anemia. In addition, the most recent transfusion episode must have occurred in the 28 days prior to study enrollment. Response in transfusion dependent patients requires absence of any PRBC transfusions during any consecutive “rolling” 12-week interval during the treatment phase, capped by a hemoglobin level of ≥ 85 g/L.

⁷ In splenectomized patients, palpable hepatomegaly is substituted with the same measurement strategy

⁸ Confirmation of spleen or liver responses by imaging studies is recommended (but not required), where a $\geq 35\%$ reduction in spleen or liver volume, assessed by magnetic resonance imaging (MRI) or computed tomography (CT), is required for confirmation. Furthermore, a $\geq 35\%$ volume reduction in the spleen or liver, by MRI or CT, constitutes a response regardless of what is reported with physical examination.

Symptoms are evaluated by the Myeloproliferative Neoplasm Symptom Assessment Form total symptom score (MPN-SAF TSS). The MPN-SAF TSS is assessed by the patients themselves and includes fatigue, concentration,

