early satiety, inactivity, night sweats, itching, bone pain, abdominal discomfort, weight loss, and fevers. Scoring is from 0 (absent/as good as it can be) to 10 (worst imaginable/as bad as it can be) for each item. The MPN-SAF TSS is the summation of all the individual scores (0-to-100 scale). Symptoms response requires $\geq 50\%$ reduction in the MPN-SAF TSS.

⁹ Confirmation by MRI or CT is recommended (but not required) to confirm progressive disease assignment for splenomegaly, where a $\geq 25\%$ increase in spleen volume from baseline is required for confirmation. Baseline values for both physical examination and imaging studies refer to pre-treatment baseline and not to post-treatment measurements.

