4.2. Primary Efficacy Endpoint

4.2.1. Definition

The primary endpoint in each arm is the overall response rate. For Arms A, B, E, and F overall response is defined to be a CI, PR, or CR noted as the objective status according to the IWG-MRT consensus criteria for MF. Response in Arm G is defined as HI, PR or CR according to the IWG criteria for MDS (Cheson et al. 2006). Response in Arm D is defined by a durable (2 months or more) decrease in peripheral blood and bone marrow blast percentage to less than 5%. The primary outcome will be the percentage of responses observed in each arm in the eligible analysis set.

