4.3. Major Secondary Endpoints

4.3.1. Definition

Spleen Response

Spleen response is defined as either a minimum 50% reduction in palpable splenomegaly of a spleen that is at least 10 cm at baseline or a spleen that is palpable at less than 10 cm but more than 5 cm at baseline becomes not palpable.

Transfusion Independence

Transfusion dependency is defined by a history of at least 2 units of red blood cell transfusions in the last month or a baseline hemoglobin level of less than 85 g/L that was not associated with clinically overt bleeding. For a transfusion dependent subject, transfusion independence is defined as he/she met either of the following conditions:

- Received no more than 1 unit of red blood cell transfusions in a rolling time interval of 30 days or more.
- Had a hemoglobin level increase over baseline more than 2g/dl if his/her baseline hemoglobin level was less than 85 g/L and received no transfusion.

Time to Response (TTR)

Time to response is defined as the duration from Study Day 1 to the earliest date that a response is first documented. For non-responders, it will be censored at the date of progressive disease/relapse or the date of the last adequate assessment, whichever comes first.

Duration of Response (DoR)

Duration of response is defined for responders as the interval from date of the initial documentation of a response to the date of first documented evidence of disease progression (or relapse for subjects who experience CR). For those subjects who are still without progression/relapse, DoR will be censored at the last adequate assessment.

Overall Survival (OS)

OS is defined as the interval from Study Day 1 to the date of death from any cause. Survival time of living subjects will be censored on the last date a subject is known to be alive or lost to follow-up.

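### SAP 4.3.1 counts relapse as a duration-of-response event only after CR, so CI and PR responders in the MF arms who lose their response without progressive disease have no event at the loss

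*SAP*

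**What the plan says.** SAP 4.2.1 defines the responders: "For Arms A, B, E, and F overall response is defined to be a CI, PR, or CR noted as the objective status" under the IWG-MRT criteria. SAP 4.3.1 then measures DoR from the first documentation of response "to the date of first documented evidence of disease progression (or relapse for subjects who experience CR"). The next sentence sets the censoring: "For those subjects who are still without progression/relapse, DoR will be censored at the last adequate assessment".

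Protocol Table 15 (Section 11.1) holds the criteria. Its relapse row has three alternatives:
- "No longer meeting criteria for at least CI after achieving CR, PR or CI, OR"
- "Loss of anemia response persisting for at least one month"
- "Loss of spleen response persisting for at least one month"

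Progressive disease is a separate row. It covers new or enlarging splenomegaly, leukemic transformation, and sustained blood blasts. Footnote 9 fixes its reference point: "Baseline values for both physical examination and imaging studies refer to pre-treatment baseline and not to post-treatment measurements".

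Protocol 16.4.4 calls for Kaplan-Meier estimation of durability but names no end event. Protocol Section 16 says the SAP takes precedence over the analyses written in the protocol.

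**The concern.** The criteria define relapse for three response categories, and the SAP uses it for one. A CI or PR responder whose benefit disappears without PD is carried as still responding until a later PD or until censoring. For those subjects the estimate labelled DoR is a time to progression.

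Durability of response is a stated secondary objective (SAP 1.1) and covers the primary and secondary endpoints. DoR is one of the two endpoints for which SAP 4.3.2 specifies a Kaplan-Meier estimate, the other being overall survival. An overstated median DoR would misdescribe how long the benefit lasts. The primary response rate and the two-stage and one-stage decision rules do not depend on DoR.

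**Working it through.** The plan gives no DoR figure to reproduce. The check compares the definitions, then illustrates the effect under assumptions.

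**Which losses of response are DoR events in the MF arms?**

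| Loss of response | Relapse in Table 15 | PD in Table 15 | DoR event in SAP 4.3.1 |
|---|---|---|---|
| CR, relapse without PD | yes | no | yes |
| CI or PR, anemia response lost for at least one month | yes | no; PD has no hemoglobin or transfusion item | no |
| CI or PR, spleen response lost for at least one month, growth below the PD threshold | yes | no | no |
| Any responder who meets PD | – | yes | yes |

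**Two cases under Table 15**

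1. *Anemia.* A transfusion-independent patient starts at 80 g/L. Response needs a rise of at least 20 g/L: 80 + 20 = 100 g/L, held for 12 weeks. Hemoglobin then returns to 80 g/L for a month. This is relapse and meets no PD criterion, so DoR keeps running.
2. *Spleen.* Baseline is 16 cm below the costal margin. Response is reached at 16 × 0.5 = 8 cm. The spleen returns to 16 cm for a month. This is relapse, but PD starts at 16 × 1.5 = 24 cm. The case assumes no qualifying imaging response, because footnote 8 says a volume reduction of at least 35% "constitutes a response regardless of what is reported with physical examination".

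**Illustration of size (every rate is an assumption)**

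Inputs:
- True median time to first failure (relapse or PD) is 12 months, so the total hazard is a = ln 2 / 12 per month.
- A share s of first failures is PD: h_p = s·a and h_r = (1 − s)·a.
- A fraction c of responders are CRs, for whom relapse counts.
- After relapse the PD hazard is b = k·h_p. Death is excluded.

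The DoR curve under the SAP rule is

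S(t) = (1 − c)·[e^(−at) + h_r·(e^(−bt) − e^(−at))/(a − b)] + c·e^(−at),

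and the median solves S(t) = 0.5. With c = 0 and k = 1, a − b = h_r, so S(t) = e^(−s·a·t) and the median is 12/s. At s = 0.5 that is 12/0.5 = 24 months.

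| PD share s | c = 0, k = 1 | c = 0.2, k = 2 |
|---|---|---|
| 1.00 | 12.0 months (1.0-fold) | 12.0 months (1.0-fold) |
| 0.90 | 13.3 (1.11) | 12.8 (1.06) |
| 0.75 | 16.0 (1.33) | 14.2 (1.18) |
| 0.50 | 24.0 (2.0) | 18.0 (1.5) |
| 0.25 | 48.0 (4.0) | 27.6 (2.3) |

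A separate simulation with c = 0, k = 1 and follow-up uniform over 24 to 60 months gave the same medians to within 0.1 month for s = 1, 0.75, 0.5 and 0.25. The share of responders with an event fell from about 0.90 under the Table 15 relapse rule to 0.82, 0.69 and 0.45 under the SAP rule at s = 0.75, 0.5 and 0.25.

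**The case against.** The best counter-argument is that the SAP uses the two terms loosely. Its time-to-response rule censors non-responders at progressive disease or relapse, although a non-responder cannot relapse. The DoR censoring sentence pairs the terms without the CR limit, and protocol Section 13 writes relapse during a dose interruption as an exception to disease progression. An analyst might therefore count any relapse.

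This shows that the text is loose, but it does not repair it. If progression already included relapse, the CR parenthesis would do nothing. Section 13 is a treatment-discontinuation rule. The censoring sentence has two readings. As shorthand for the event just defined, it censors relapsed CI and PR responders after their response was lost. Taken literally, it leaves them with neither an event nor a censoring rule.

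Several narrower points stand:
- A CI or PR responder who relapses and later meets PD does have an event, but later than the loss.
- For a baseline spleen of 5 to 10 cm, regrowth from non-palpable might be scored as new splenomegaly and hence PD. Footnote 9 points the other way. The 16 cm case is free of this doubt.
- SAP 4.3.1 would class the 80 g/L patient as transfusion dependent. Table 15 governs overall response, so the case holds there. A baseline of 90 g/L rising to 110 and falling back to 90 avoids the conflict.
- The lower figures in the illustration are not bounds. With c = 0.4 and k = 5 the inflation is 1.19-fold at s = 0.5 and 1.5-fold at s = 0.25.
- DoR is descriptive and responders are few: 30% of the 33 combined Arm A–C patients is about 10. Listings of response status, transfusions and spleen would still show the losses that were collected.
- Arm G is largely protected. Table 16 counts falls in blood counts and hemoglobin as progression, and Table 17 merges progression with relapse.

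**Conclusion.** The concern holds. As written, CI and PR responders in the MF arms who relapse without PD have no DoR event at the loss, and nothing else in the SAP or protocol supplies one. The direction is certain: for an affected subject, recorded DoR equals or exceeds the time in response.

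The size is not known. It depends on the CR share, the split of first failures between relapse and PD, and the PD hazard after relapse, none of which the documents give. It is zero if every first failure is PD. The fold-changes above rest wholly on assumed constant hazards and should be read as illustration. Because the endpoint is secondary and descriptive, this is a definition to correct before reporting; it does not threaten the primary result.

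**What to change.** In SAP 4.3.1, delete the CR limit and define the end of DoR, for every responder (CR, PR or CI, and HI in Arm G), as the earlier of disease progression or relapse by the protocol Section 11 criteria. Reword the next sentence so that subjects with neither event, so defined, are censored at their last adequate assessment.

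Three related points are worth stating in the same edit, although they are not part of the error:
- whether relapse during a planned dose interruption counts as a DoR event;
- which event ends response in Arm D;
- whether death without progression or relapse stays censored, as the present text implies.

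The cost is two SAP sentences and a modest re-derivation, and the reported median may be shorter. Relapses after Cycle 9 may be captured less completely, because protocol Table 3 does not require spleen palpation, transfusion review or IWG response in extension cycles, even though Section 8.1 says efficacy is evaluated each cycle. Blood counts continue in every extension cycle, and event monitoring records first relapse or progression. No new data collection is needed, but the report should state this limit.

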The International Prognostic Scoring System (IPSS), used for risk stratification in PMF, uses risk factors assessed at time of diagnosis: age >65 years, constitutional symptoms, hemoglobin < 10 gm/dL, leukocyte count $>25 \times 10^9/L$ and peripheral blood blasts $\geq 1\%$ (Tefferi 2011). Subsequently, the IPSS prognostic variables were used to devise a dynamic IPSS (DIPSS) that can be utilized at any point during the disease (Tefferi 2011). Most recently, DIPSS was further revised to DIPSS-plus by the incorporation of 3 additional IPSS/DIPSS-independent risk factors, including red cell transfusion need, platelet count $<100 \times 10^9/L$, and unfavorable karyotype (Tefferi 2011); the latter includes complex karyotype or sole or 2 abnormalities that include +8, -7/7q-, i(17q), inv(3), -5/5q-, 12p-, or 11q23 rearrangement. The 8 DIPSS-plus risk factors are currently used to define low (no risk factors), intermediate- 1 (1 risk factor), intermediate-2 (2 or 3 risk factors), and high (≥ 4 risk factors) risk groups with respective median survivals of 15.4, 6.5, 2.9, and 1.3 years (Tefferi 2011). Patients with MF can progress into blast phase disease (BP-MF), defined by the same criteria used by WHO for acute myeloid leukemia (AML) (i.e. 20% or more blasts in the peripheral blood or bone marrow). Some patients with MPN share certain morphologic features with those with myelodysplastic syndromes (MDS). The WHO classifies such cases as MDS/MPN overlap and their clinical features are similar to patients with MF (i.e. severe anemia, splenomegaly, leukocytosis and thrombocytosis).

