11.2. MDS

The International Working Group response assessment as reported by [Cheson et al. \(2006\)](#) will be utilized.

Table 16: Definition of Disease Response in MDS:

Category	Response Criteria
Complete Remission (CR)	
Bone marrow: $\leq 5\%$ myeloblasts with normal maturation of all cell lines¹
 
Persistent dysplasia will be noted^{1,2}
 
Peripheral blood³
 
 Hgb ≥ 11 g/dL Platelets $\geq 100 \times 10^9/L$ Neutrophils $\geq 1.0 \times 10^9/L^2$ Blasts 0%
Partial Remission (PR)	
All CR criteria if abnormal before treatment except:
 
Bone marrow blasts decreased by $\geq 50\%$ over pretreatment but still $> 5\%$
 
Cellularity and morphology not relevant

Stable Disease (SD)	Failure to achieve at least PR, but no evidence of progression for > 8 weeks
Failure (FAIL)	Death during treatment or disease progression characterized by worsening of cytopenias, increase in percentage of bone marrow blasts, or progression to a more advanced MDS FAB subtype than pretreatment
Relapse after CR or PR	
At least 1 of the following:
 
 Return to pretreatment bone marrow blast percentage Decrement of $\geq 50\%$ from maximum remission/response levels in granulocytes or platelets Reduction in Hgb concentration by ≥ 1.5 g/dL or transfusion dependence

Category	Response Criteria
Disease Progression (PD)	
For patients with:
 
 Less than 5% blasts: $\geq 50\%$ increase in blasts to $> 5\%$ blasts 5%-10% blasts: $\geq 50\%$ increase to $> 10\%$ blasts 10%-20% blasts: $\geq 50\%$ increase to $> 20\%$ blasts 20%-30% blasts: $\geq 50\%$ increase to $> 30\%$ blasts 
Any of the following:
 
 At least 50% decrement from maximum remission/response in granulocytes or platelets Reduction in Hgb by ≥ 2 g/dL Transfusion dependence

¹ Dysplastic changes should consider the normal range of dysplastic changes (modification).

² Modification to IWG response criteria.

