16. STATISTICAL CONSIDERATIONS AND METHODOLOGY

Overview: This protocol will assess the efficacy of different schedules of imetelstat in six cohorts of patients with myelofibrosis (including blast-phase disease in Arm D) and one cohort of patients with MDS/MPN or MDS with spliceosome mutations or ring sideroblasts using a phase II study design in each arm independently.

Descriptive statistics will be used to summarize baseline patient characteristics, treatment administration, efficacy, and safety outcomes. Descriptive summaries of discrete data will present the number of patients and the incidence as a frequency and as a percentage. Descriptive summaries of continuous data will present the group mean, standard deviation, median, minimum, maximum, and sample size.

For regulatory reporting purposes, there are two time points for the analyses: (1) the primary analysis 48 weeks after the last patient has been enrolled, and (2) the final analysis after all patients have completed the study. A separate and detailed statistical analysis plan (SAP) developed prior to primary analysis will supersede analyses specified in the protocol. Deviations from the SAP will be noted in the final study report.

Primary Endpoint: The primary endpoint in each arm of this trial is overall response rate. Overall response will be defined as a CI, PR, or CR (for Arms A, B, C, E, and F) according to the IWG-MRT consensus criteria for MF, or as a HI, PR or CR (for Arm G) according to the IWG consensus criteria for MDS, or the achievement of <5% peripheral blood and bone marrow blast % that lasts for at least two months (for Arm D).

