16.4.4. Durability of Response

Durability overall response will be estimated using the Kaplan-Meier method. Approximate 95% confidence intervals for median duration of response will be computed using the formula proposed by Brookmeyer and Crowley. The same method will be applied to hepatosplenic response and anemia response for Arms A, B, E, F, and D and erythroid response for Arm G.

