4.3.2. Analysis Methods

Subjects' status of spleen response and transfusion-independence will be listed for all eligible subjects.

Duration of response will be estimated using the Kaplan-Meier method. Approximate 95% confidence intervals for median duration of response will be computed using the formula proposed by Brookmeyer and Crowley. The same method will be applied for OS.

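### The SAP does not count death as a duration-of-response event, so responders who die without documented progression are censored and the median is expected to run long

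*SAP*

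**What the plan says.** SAP 4.3.1 starts DoR at the first documentation of response and runs it "to the date of first documented evidence of disease progression (or relapse for subjects who experience CR"). The censoring rule follows: "For those subjects who are still without progression/relapse, DoR will be censored at the last adequate assessment". Neither sentence mentions death, and the second is not limited to living subjects. The same section does name death where it is meant to be an event: "OS is defined as the interval from Study Day 1 to the date of death from any cause".

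On method, SAP 4.3.2 says "Duration of response will be estimated using the Kaplan-Meier method", with Brookmeyer-Crowley limits for the median. It gives no competing-risk analysis and no sensitivity analysis.

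Protocol 16.4.4 says only "Durability overall response will be estimated using the Kaplan-Meier method", with the same type of interval and no list of events. Protocol section 16 adds that the SAP "will supersede analyses specified in the protocol", so the SAP definition governs.

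**The concern.** Kaplan-Meier treats a censored subject as someone who could still have the event later, at the same rate as those still followed. A responder who has died cannot go on responding. Censoring that person makes the curve describe response in a setting without death, while a reader will take the median as how long responses lasted.

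This matters here for three reasons.

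- Onset and durability of response in each arm is a stated secondary objective (Protocol 2.2, SAP 1.1).
- Survival is short. Arms A, B, E and F take intermediate-2 or high-risk MF, and Protocol 1.1 gives the four DIPSS-plus groups, from low to high risk, "respective median survivals of 15.4, 6.5, 2.9, and 1.3 years". Protocol 1.4.1 calls the prognosis poor for the patients in Arms D and G.
- Death without a recorded progression is plausible. Protocol Table 3 schedules IWG response assessment in Cycles 1–9 but not in the Extension Phase, and later event monitoring may be done by telephone. In the other direction, Protocol 8.1 still asks for an efficacy evaluation at the end of each cycle in both phases.

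Only 80 patients were enrolled across all arms, so each arm has few responders. Reclassifying one or two deaths can move a median.

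**Working it through.** The plan states no expected DoR, event count or DoR power, so there is no figure of its own to reproduce. The check has three parts.

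**1. Does any other text supply death as an event?**

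- Protocol Table 15 (MF) defines progressive disease and relapse by spleen size, blasts and loss of response. Death is not included.
- Protocol Table 16 (MDS) defines relapse and disease progression without death. Death appears only under Failure: "Death during treatment or disease progression characterized by worsening of cytopenias". The DoR definition does not use that category.
- Protocol 16.4.4 and SAP 4.3.2 give an estimator, not events.

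No other text supplies it.

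**2. Expected size, illustrative.**

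Inputs from the documents: median survival S = 2.9 × 12 = 34.8 months (intermediate-2) and 1.3 × 12 = 15.6 months (high risk), from Protocol 1.1.

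Assumptions: constant hazards; progression median m = 12 or 18 months; a share f = 0.25, 0.5 or 1 of the group's death hazard acting before documented progression.

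- Median under the SAP rule: ln 2 / (ln 2 / m) = m.
- Median with death counted: ln 2 / (ln 2 / m + f × ln 2 / S) = m / (1 + f × m / S).
- Overstatement: f × m / S.

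Example with m = 18, S = 15.6, f = 1: 18 / (1 + 18/15.6) = 18 / 2.154 = 8.4 months, and 18/15.6 = 115%.

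| S (months) | f | m = 12: with death counted | Overstatement | m = 18: with death counted | Overstatement |
|---|---|---|---|---|---|
| 34.8 | 0.25 | 11.0 | 9% | 15.9 | 13% |
| 34.8 | 0.5 | 10.2 | 17% | 14.3 | 26% |
| 34.8 | 1 | 8.9 | 34% | 11.9 | 52% |
| 15.6 | 0.25 | 10.1 | 19% | 14.0 | 29% |
| 15.6 | 0.5 | 8.7 | 38% | 11.4 | 58% |
| 15.6 | 1 | 6.8 | 77% | 8.4 | 115% |

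With f = 0 the overstatement is 0%. The formula is linear in m, so the range depends on the progression medians chosen.

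**3. Behaviour in a small arm.**

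A simulation used 7 responders, assessments every 3 months, administrative censoring between 24 and 48 months, m = 12, 18 or 24 and f = 0.5 or 1. The typical Kaplan-Meier median under the SAP rule was equal to or longer than the median with death counted in every scenario, for example 18 against 9 months at m = 18, S = 15.6, f = 1. The SAP-rule median was not reached in 2–40% of runs, against 0–7% with death counted.

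That simulation puts all responders on one visit grid. No progression can then be recorded between a responder's last assessment and death, so a reversal cannot occur. Off such a grid it can. Take five responders: two last assessed at month 10 who die at month 14, and three who progress at months 11, 12 and 20.

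- SAP rule: both deaths are censored at 10, leaving three at risk. S(11) = 2/3 and S(12) = 2/3 × 1/2 = 1/3. Median 12 months.
- Death counted: S(11) = 4/5, S(12) = 4/5 × 3/4 = 3/5, S(14) = 3/5 × 1/3 = 1/5. Median 14 months.

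Here the SAP rule gives the shorter median, because it removes the dead responders from the risk set before their date of death.

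**The case against.** The strongest reply is that little depends on this endpoint. The primary endpoint is response rate, the decision rules in Protocol 16.1 count responses only, SAP 1.3 calls the trial a pilot, and no hypothesis or power is attached to DoR. That stands, and it limits the severity.

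Second, a duration ended only by progression or relapse is a legitimate cause-specific quantity and is consistent with Table 15. That also stands, but the SAP does not label it so and offers no companion analysis. OS is estimated (SAP 4.3.2), deaths are tabulated by arm and cause (SAP 5.2), and response status is listed by cycle (SAP 4.2.2). These let a reader see the deaths; they do not correct the DoR median.

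Third, some deaths may already count. Protocol 10.3.1.5 has a death attributed to MF progression recorded under a progression term, and 10.3.1.7 treats worsening MF as efficacy data. Such a death might be read as documented progression. The SAP does not say so, and deaths from other causes would still be censored.

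Fourth, the size is not taken from the documents. The survival figures are for whole risk groups, include deaths after progression, and may not fit responders. This stands.

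A reader might also infer from the Failure entry in Table 16 that the protocol already ends a response at death and the SAP contradicts it. The table does not support that. Failure is a response category for Arm G, listed apart from relapse and disease progression, and it does not define when a response ends.

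**Conclusion.** The concern holds as an expected upward bias in a descriptive secondary endpoint and should be fixed. The direction in expectation follows from the rule: if any responders die before documented progression, the Kaplan-Meier median targets a longer duration than the one ended by progression or death.

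The 9–115% range for the MF arms rests on constant hazards, the two assumed progression medians and the assumed mortality share. A share of 100% lets all of the risk group's mortality act before progression and is an upper bound. The lower limit is 0%. The documents give no survival figure from which to work for Arms D and G.

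Two stronger readings are tempting and do not hold. One is that censoring deaths always lengthens, or never shortens, the reported DoR. It has no effect if no responder dies first, and the five-responder example shows a reversal. The other is that the flaw undermines the trial's conclusion on activity. It does not reach the response rates, their exact intervals or the go/no-go rules.

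**What to change.** In SAP 4.3.1, define the end of DoR as the earliest of documented progression, relapse or death from any cause. Censor at the last adequate assessment only subjects who are alive without an event. If the progression/relapse-only duration is wanted, show it as supportive, labelled as such, with death handled as a competing event.

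Whether relapse should count only after CR, as the SAP has it, or also after PR or CI, as in Table 15, is a separate question that this change does not settle.

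The cost is small: a change to the wording of one definition. Death dates are already needed for OS, and SAP 2.3 already has imputation rules for partial ones. The downside is that reported DoR will probably be somewhat shorter.
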